Biochemistry blood test: Sodium (Na), Potassium (K), Chloride (Cl), Creatinine, Glucose, Urea, Albumin, Calcium total, Alkaline Phosphatase (ALP), ALT, AST, Total Bilirubin, Direct Bilirubin, LDH, Total Protein, Uric Acid, CRP, and Lipid Profile (including Total Cholesterol, HDL, LDL, Triglycerides).

Hematology blood test: complete CBC.

D-Dimer test (coagulation): one tube for coagulation test

Inflammatory markers: the blood will be centrifuged and frozen according to the Lab manual, Local Lab.

Vital signs: blood pressure, pulse, weight, weight, body temperature (PO), saturation, respiratory rate.

VAS scale: will be performed by study staff member.

WHO Ordinal Score: will be completed by the study staff member based on patient status.

COVID-19-Related Symptoms assessment: will be completed by the study staff member based on patient status and answers.

COVID-19–Impact on Quality-of-Life Questionnaire: will be completed by the study staff member based on patient answers.

	MGC Pharma Clinical Study Protocol	Protocol No.: MGC-009
		Version 02, 05 Sep 2021
		Page 40 of 76
A Phase IIb, double blind, placebo-controlled clinical study designed to evaluate the effect of CimetrA in patients diagnosed with COVID-19		CONFIDENTIAL

POST- COVID-19 Functional Status Scale: will be completed by the study staff member based on patient answers.

Pregnancy test: women of childbearing potential must undergo a urine pregnancy test.

Physical examination: full examination by doctor.

** Measurements will be performed per institutional schedule by the hospital staff, not necessarily by the principal investigator or the sub-investigators.

PK parameters*: will be performed only on 14 patients that will agree to participate in the PK analysis (only for Brazil and South Africa).

The PK will be performed only for the first dose of drug, after patient received the first dose (5 puffs) the study staff need to follow the table below.

For each test, approximately 5 ml of blood will be drawn (equivalent to one teaspoon) total of 55 ml of blood will be drawn.

Table 6: List of time points for pharmacokinetic assessments

Study Visit Number 1	
Time point 0	Dosing (before the first dose of the drug)
Time Point 1	15 minutes post dose
Time Point 2	30 minutes post dose
Time point 3	45 minutes post dose
Time point 4	1 h post dose
Time point 5	1.5 h post dose
Time point 6	2 h post dose
Time point 7	4 h post dose
Time point 8	6 h post dose
Time point 9	8 h post dose

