11.3. Removal of subjects from therapy or assessment

- a. If any of the inclusion criteria fails to be met, or any of the exclusion criteria is met during the period in which the interim history, physical examination and laboratory tests are performed, the subject will be ineligible to continue in the study. These subjects will be classified as screened but not enrolled.
- b. If the subject begins a regimen of medication at any time during the study that includes any of the medications listed in the exclusion criteria or begins an increase in dose of an existing regimen of medication at any time during the study, the subject will be terminated from the study. These subjects will not be used in the primary analyses.
- c. If continuing in the study does not appear to be in the best medical interest of the subject, his/her participation may be terminated by either the Principal

	MGC Pharma Clinical Study Protocol	Protocol No.: MGC-009
		Version 02, 05 Sep 2021
		Page 48 of 76
A Phase IIb, double blind, placebo-controlled clinical study designed to evaluate the effect of CimetrA in patients diagnosed with COVID-19		CONFIDENTIAL

Investigator or the study director. Removal of an individual by the Principal Investigator will be reported to the Institutional Helsinki Committee and the appropriate regulatory agencies according to the guidelines of these groups. These subjects will not be used in the primary analyses unless the reason for removal was due to reasons of safety in which case data would be used in the primary analyses.

d. In addition to a participant being able to voluntarily withdraw from the study at any time, the Investigator may withdraw participants from the study under the conditions noted below, and such subjects will not used in the primary analyses.

e. Participants will be withdrawn from the treatment protocol if participants are unwilling or unable to comply with the schedule of treatment, follow-up or safety monitoring, and will not be used in the primary analyses.

f. Subjects considered treatment failures will be removed from the study and will be offered alternative standard therapy by their treating physician and will not be used in the primary analyses.

11.4. **Screening and Enrollment logs**

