17. STATISTICAL METHODS AND DETERMINATION OF SAMPLE SIZE

A prospective, randomized (1:1:1), double-blind, multi-center, placebo-controlled clinical study.

Statistical Hypothesis

The hypothesis of this study is that treating with CimetrA and CimetrA2 will be more effective, while maintaining a favorable safety profile. This will be demonstrated by a significant difference between the two active and the control groups.

	MGC Pharma Clinical Study Protocol	Protocol No.: MGC-009
		Version 02, 05 Sep 2021
		Page 60 of 76
A Phase IIb, double blind, placebo-controlled clinical study designed to evaluate the effect of Cimetra in patients diagnosed with COVID-19		CONFIDENTIAL

In this study, we will test the following hypothesis:

- H0: $\Delta_1 = \Delta_2 = \Delta_3$
- H1: at least one is different.

Where Delta is the difference between baseline and end of study in WHO Ordinal Scale for clinical trial.

If the null hypothesis is rejected in favor of the alternative hypothesis the study will be deemed successful.

Safety will be assessed by adverse events, blood and urine laboratory assessments and vital signs.

Planned Sample Size

For this phase IIb, 3-armed clinical trial, we use the ANOVA test to estimate the expected improvement in the primary outcome; the WHO ordinal scale for clinical improvement.

We expect medium effect ($f=0.20$) for the differences in Delta between the 3 groups, and standard deviation of 1.5, based on the ordinal scale (0-8). This power analysis is for a one-way fixed effects analysis of variance with 3 levels. The study will include 80 patients per group for a total of 240 patients.

The criterion for significance (α) has been set at 0.05 with Power of at least 80%.

The analysis of variance is two-tailed Main effects.

For immunogenicity assessment, larger sample size will reduce mean variability in the observed outcomes and will increase the opportunity to detect real changes.

For 80 participants per group we ensure the desired precision for phase 3 trial to assess safety and effectiveness. Total sample 240 patients.

Computer Software

	MGC Pharma Clinical Study Protocol	Protocol No.: MGC-009
		Version 02, 05 Sep 2021
		Page 61 of 76
A Phase IIb, double blind, placebo-controlled clinical study designed to evaluate the effect of CimetrA in patients diagnosed with COVID-19		CONFIDENTIAL

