Sample size and Power were calculated with the Power and Precision statistic program ver 4.1 and all statistical analyses and data presentations, including tabulations and listings, will be performed using the SPSS statistic program version 27.0 (or higher) software.

Randomization

Randomization tend to produce study groups comparable with respect to known and unknown risk factors, removed investigator bias in the allocation of participants and guarantees that statistical tests will have valid false positive error rates.

After a participant will meet the eligibility criteria, he/she will be randomly allocated (with a 1:1:1 ratio) to one of the following treatment groups based on a randomization scheme stratified by center.

The randomization scheme will be prepared by an independent statistician using statistic program for random number generator. The block size is set in ahead and study personnel will be blinded to the randomization block size.

Blinding

This is a double-blind study: neither the participants nor the investigators will be aware of arm allocation of each study participant.

Blindness is important to avoid bias. Monitoring and reporting of the success of blindness are important for the reader's confidence of the trial results. Groups should be marked by capital letter and blindness should maintain throughout the study.

Missing Data

Safety data should be collected from non-adherent/withdrawal participants to avoid possible bias.

	MGC Pharma Clinical Study Protocol	Protocol No.: MGC-009
		Version 02, 05 Sep 2021
		Page 62 of 76
A Phase IIb, double blind, placebo-controlled clinical study designed to evaluate the effect of Cimetra in patients diagnosed with COVID-19		CONFIDENTIAL

Prior to analyzing the data, extreme laboratory values should be checked. Missing values will be treated as ITT.

Multiple imputation for binary data will be used as the primary imputation method in the case of missing data for the primary efficacy endpoint.

Dropout/AE Imputation: A participant with no post baseline measurement or a participant withdrawn due to an adverse event or treatment intolerability will use last observation carried forward imputation methods.

Baseline Data

Baseline participant characteristics will be collected at screening. The specific baseline (“start of treatment”) endpoints and other symptoms will be collected prior to each treatment.

Significance Levels and Handling of Type I Error

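### The protocol does not require the WHO score through Day 28 from patients removed under section 11.3, so the primary outcome can be lost selectively

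*Protocol*

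**What the plan says.** - **Collection after withdrawal.** Section 17, Missing Data: "Safety data should be collected from non-adherent/withdrawal participants to avoid possible bias". No efficacy measurement is named there or elsewhere for these participants.
- **Removal.** Section 11.3 covers removal from therapy and from assessment under one title. Under item b, for certain medication changes, "the subject will be terminated from the study". Under item f, "Subjects considered treatment failures will be removed from the study and will be offered alternative standard therapy". Item e is narrower and withdraws the non-compliant from the treatment protocol.
- **Analysis of removed patients.** Section 11.3 keeps items b, d, e and f out of the primary analyses, and item c as well unless the reason was safety. Section 17 instead runs efficacy on both the ITT and PP sets. It names multiple imputation (worded for binary data) for a missing primary endpoint, and adds that a participant with no post-baseline measurement or "a participant withdrawn due to an adverse event or treatment intolerability will use last observation carried forward imputation methods".
- **Follow-up.** Section 10 and the end of section 10.2.1 continue follow-up to Day 28 at any location, but in the case of hospital discharge.
- **Measurement.** Table 5 schedules the WHO score on Days 1, 7, 14, 21 and 28, with Day 21 by phone. The notes to Table 5 add: "WHO Ordinal Score: will be completed by the study staff member based on patient status".

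**The concern.** The protocol recognises that losing withdrawn and non-adherent participants can cause bias, but the remedy it names covers safety data and not the primary outcome. Treatment lasts two days and the endpoint is change to Day 28, so most reasons for removal can arise when no dosing is left to stop. Several are linked to how the patient is doing. Treatment failure is linked by definition. An increased dose of an existing medication is linked in practice, because sections 10 and 13.2 allow steroids, anticoagulants and other standard care by clinical judgement.

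A site that follows items b and f has no WHO score due after removal. The scores would then be missing mainly in patients doing badly. This is a data-collection rule: no analysis plan can recover a score that nobody recorded.

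**Working it through.** **Inputs from the protocol (section 17).** Three arms of 80, one-way ANOVA, "We expect medium effect ($f=0.20$) for the differences in Delta between the 3 groups, and standard deviation of 1.5". Significance level and power: "The criterion for significance (α) has been set at 0.05 with Power of at least 80" percent. No dropout allowance and no removal rate are given, so every rate below is an assumption.

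**1. The plan's own figure.** Noncentrality = N × f² = 240 × 0.20² = 9.6, with 2 and 237 degrees of freedom. Power is 79.3%, which agrees with the stated 80% to within a point (82 per arm would reach 80%). The SD of the arm means is 0.20 × 1.5 = 0.30. The spread between the highest and lowest arm is therefore 0.30 × 3/√2 = 0.64 points if one arm differs from the other two, and 0.30 × √6 = 0.73 if the means are evenly spaced. The 80% rests on all 240 patients contributing a score.

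**2. Power when scores are lost (equal loss d in every arm).**
- Removed patients left out, d = 10%: 72 per arm, noncentrality 216 × 0.04 = 8.64, power 74.6%. At d = 20%, power is 69.1%.
- Removed patients kept at zero change (SD held at 1.5), d = 10%: f = 0.20 × 0.90 = 0.18, noncentrality 240 × 0.0324 = 7.78, power 69.9%. At d = 20%, power is 58.9%.

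**3. False rejection under unequal removal, ITT reading.** A patient removed before Day 7 has only the baseline WHO score, so carrying it forward records zero change. With no true effect, mean change m in all arms, and 5% removed on placebo against 15% on each active arm, the false difference is |m| × (0.15 − 0.05). Simulated rejection rates of the F test (3 × 80, SD 1.5; ranges across repeat runs of 10,000 to 40,000 trials):

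| Mean change m | False difference | Rejection |
|---|---|---|
| -1 | 0.10 | 6.5 to 7.0% |
| -1.5 | 0.15 | 8.8 to 9.4% |
| -2 | 0.20 | 12.4 to 12.9% |
| -2.5 | 0.25 | 14.9 to 15.4% |

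Other cases:
- 5/10/10% removal: about 5.5% at m = -1 and 7.5 to 7.9% at m = -2.5.
- Equal removal of 10% in every arm: about 5%.
- 5/15/15% removal, m = -2.5, with half the change already carried forward (mean -1.25, SD 1.5): about 7.5%.

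This false difference counts against the active arms. Reversing the removal rates reverses its sign.

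**4. Exclusion reading (11.3f).** Suppose failures change by +2, everyone else by -2.5, and 15% fail on placebo against 10% on active.
- Active mean: 0.10 × 2 − 0.90 × 2.5 = -2.05.
- Placebo mean: 0.15 × 2 − 0.85 × 2.5 = -1.825.
- True difference: -0.225.

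With failures left out, both arms average -2.5 and the difference is 0. The example is built so that all the benefit comes through fewer failures. It shows the direction of the error and does not estimate its size.

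**The case against.** A reader might infer that the protocol limits collection to safety data, so that Day 28 scores will not exist. The text does not go that far. The Missing Data sentence does not say that nothing else may be collected, Table 5 schedules the score without an exception, and item 11.3e ends only the treatment protocol. Deaths and life-threatening events would also reach the database as serious adverse events. What stands is that nothing requires the score after removal, and that items b and f end participation.

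A reader might also infer that the primary result rests on carried-forward or imputed values. Section 11.3 says the opposite for items b, d, e and f, which are left out. Imputation follows only from the ITT wording of section 17, and the protocol does not say which section governs. Nor does it carry treatment failures forward in general: that rule covers adverse-event or intolerability withdrawals and participants with no post-baseline measurement. A calculation that sets every failure to zero change therefore matches no stated rule.

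Three further points weaken the concern:
- The 15% is the top of a range. It needs removal three times as frequent on active, zero carried-forward change and a mean change of -2.5. If removed patients are simply dropped and removal is unrelated to outcome, rejection is 4.8%.
- Item b refers to medications in the exclusion criteria, which list none, so only its dose-increase part operates.
- Section 17 plans a missing-data sensitivity analysis, whose method may properly sit in the SAP. It can show how fragile the result is, but it cannot replace the missing scores.

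**Conclusion.** The point holds in this form: the protocol does not require the WHO score through Day 28 from patients removed under section 11.3, and the loss is likely to depend on outcome because treatment failure is a reason for removal. Sections 11.3 and 17 also disagree on whether these patients are left out or imputed, and the true score is absent either way.

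The bias cannot be sized from the documents. On the stated assumptions, false rejection ranges from about 5% with equal removal to about 15% in the least favourable case shown. Power falls from 79.3% to between 69.9% and 74.6% at an assumed 10% loss. The documents do not support saying that the scores will certainly be missing, or that the primary result rests on imputed values.

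**What to change.** 1. In section 17, Missing Data, add that for every randomised participant who has not withdrawn consent to follow-up, the WHO Ordinal Score (including death) and oxygen, ventilation and ICU status are recorded on Days 7, 14, 21 and 28, by phone or from the hospital record, whatever happened to study treatment.
2. In section 11.3, separate stopping study treatment from leaving follow-up, so that only withdrawal of consent to follow-up ends outcome collection. Who stops treatment, and why, is not affected.
3. Reconcile the section 11.3 exclusions with the ITT analysis in section 17. Without this, the collected scores could still go unused.

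The cost is protocol wording and a few extra phone calls or chart checks. Staff already score the scale from patient status, and already do so by phone on Day 21. No new procedure and no additional patients are needed.
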